RVVC is likely a multifactorial disease including genetic predisposition to enhanced vaginal colonization where, in the presence of secondary triggering mechanisms, the carrier state is transformed into a proinflammatory state by a host's hyperactive local immune response. Long-term antifungal suppressive therapy may help control the host's mucosal reaction by keeping the vaginal fungal load at markedly reduced levels.⁴ Several long-term maintenance regimens using either topical azoles or oral azoles (e.g., ketoconazole, itraconazole, and fluconazole) have been studied showing benefit in preventing recurrences of VVC. Although there have been few comparative studies, the best results were obtained with long-term maintenance therapy using once weekly fluconazole 150 mg for 6 months.^{5,6} The most important limitation of the suppressive therapy with fluconazole is exactly that: suppression of growth rather than eradication of the yeast. Even though yeast organisms are dramatically reduced in number, below the level of detection by conventional culture technique, they persist in low numbers in the vaginal lumen, triggering the VVC episode upon discontinuation of fluconazole. A fungicidal drug and regimen may be able to address this significant limitation of current therapies for RVVC and may be associated with a more sustained benefit after discontinuation of therapy.

This study aims to demonstrate the efficacy and define the safety of a 6-month dosing regimen of oral ibrexafungerp to prevent recurrences in subjects with RVVC.

The glucan synthesis inhibitor ibrexafungerp

Ibrexafungerp (SCY-078) is a member of a new class of antifungal agents and is an orally active, semi-synthetic, triterpene derivative of the natural product enfumafungin. Ibrexafungerp is a

structurally distinct class of glucan synthesis inhibitor that inhibits the synthesis of the fungal cell wall polymer β -(1,3)-D-glucan. Time-kill studies have demonstrated that ibrexafungerp has *in vitro* fungicidal activity against *Candida* spp. isolates similar to that observed with the echinocandins.

Ibrexafungerp is being developed as the first oral and intravenous (IV) glucan synthesis inhibitor for the treatment and prevention of fungal infections caused by *Candida* and *Aspergillus* species with the potential to provide the therapeutic advantages of both an IV and oral formulation.

Antifungal activity

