The *in vitro* studies indicated that ibrexafungerp metabolism was predominantly oxidative, with cytochrome P450 (CYP) 3A being the primary enzyme involved in its oxidative metabolism. Strong inhibitors of CYP3A would be expected to increase plasma levels of ibrexafungerp; therefore, the concurrent administration of ibrexafungerp with such inhibitors is prohibited.

Clinical experience

To date, over 500 subjects and patients have received either oral or IV formulations of ibrexafungerp in Phase 1 and Phase 2 studies. Ibrexafungerp was generally well tolerated following single oral doses of up to 1600 mg and multiple oral doses of up to 800 mg/day for 28 consecutive days in Phase 1 studies. Reported adverse events (AEs) after oral administration have been generally transient and primarily mild to moderate in intensity. The most frequently reported AEs have been mild gastrointestinal events (nausea, vomiting, diarrhea and abdominal pain).

A Phase 2 study of oral ibrexafungerp as step-down therapy from IV echinocandin in patients with invasive candidiasis has been completed. Following three to ten days of IV echinocandin therapy, 21 patients received either ibrexafungerp or fluconazole. Ibrexafungerp was well tolerated, with an AE profile typical of this population, with the most common treatment-related AEs being gastrointestinal in nature (i.e., nausea and diarrhea). The results from this study also indicated that the higher dose of ibrexafungerp tested (750 mg once a day [QD]) is predicted to achieve the target exposure at steady state in the majority of patients.

A Phase 2 proof-of-concept study of oral ibrexafungerp in patients with acute VVC has also been completed. In this multicenter, randomized, active-controlled, evaluator-blinded study of oral ibrexafungerp compared to oral fluconazole in adult female patients with acute VVC, 96 patients with an acute, moderate to severe, symptomatic episode of vulvovaginal candidiasis were randomized at a 1:1:1 ratio to receive either oral ibrexafungerp 750 mg with a 1250 mg loading dose for three days, oral ibrexafungerp 750 mg with a 1250 mg loading dose for five days or a single dose of oral fluconazole. Ibrexafungerp was well tolerated, with the most common AEs

being mild gastrointestinal events. The high clinical cure rates observed in this study are supportive of the clinically relevant antifungal activity of ibrexafungerp in this form of *Candida* infection.

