Several drug-drug interaction studies have been conducted. Ketoconazole (a strong inhibitor of CYP3A) induces a significant (5-fold) increase in ibrexafungerp exposure, while diltiazem (a moderate inhibitor of CYP3A) induces a mild to moderate (< 3-fold) increase in ibrexafungerp exposure. Ibrexafungerp did not have any effect on rosiglitazone (a CYP2C8 substrate) exposure, had only a mild effect (less than a 0.5-fold increase) on the area under the curve of tacrolimus (a CYP3A and P-glycoprotein [P-gp] substrate) and had no effect on the maximum concentration (C_{max}) of tacrolimus.

Ibrexafungerp has the potential to be an important addition to the antifungal treatment arsenal by providing potent activity against the full spectrum of *Candida* species, including difficult-to-treat organisms, and by affording the added flexibility of both oral and IV formulations.

For additional information on Ibrexafungerp (SCY-078), please refer to the Investigator's Brochure (IB).

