- **Prevention of Recurrence Phase:** The occurrence of a recurrence is the key efficacy parameter in this study. Subjects who have a culture-confirmed *Candida* spp. infection from the sample collected at Screening, achieve significant resolution of their vulvovaginal signs and symptoms (defined as a total composite score ≤ 2 on the VSS Scale) at Baseline (Day 1) and continue to meet all other eligibility criteria will be randomized into the Prevention of Recurrence Phase. Subjects who are not eligible for this study or the Nested Sub-Study will be discontinued. Subjects will be assessed for potential recurrences throughout the Study Treatment Period and the Follow-up Period.
 - **Study Treatment Period (Baseline [Day 1] through Week 24 [TOC]):** Subjects will be randomized at a 1:1 ratio to receive one of two study treatments (oral ibrexafungerp or placebo administered as a single-day treatment repeated every 4 weeks [28 days (± 3)] for a total of 6 single-day treatments) in a double-blind manner. Each single-day treatment will consist of two doses of ibrexafungerp 300 mg each or placebo given 12 (± 4) hours apart (total single-day ibrexafungerp dose = 600 mg). Subjects will take the study drug on Day 1 (Baseline), Week 4, Week 8, Week 12, Week 16 and Week 20, regardless of recurrence or administration of antifungal medication. Subjects will be evaluated for potential recurrence, antifungal medication use and safety throughout this period.
 - **Follow-up Period (Week 25 through Week 36 [EOFU]):** Subjects will enter the Follow-up Period regardless of recurrence or rescue antifungal medication use. Subjects will continue to be evaluated for potential recurrence, antifungal medication use and safety throughout this period.

Efficacy and Safety

Efficacy will be determined primarily by the percentage of subjects with documented Clinical Success (defined as subjects having a TOC evaluation and no Mycologically Proven, Presumed or Suspected recurrence of VVC) up to TOC (Week 24). The key secondary endpoint will be the percentage of subjects with no Mycologically Proven Recurrence (defined as an episode of VVC with a total composite score ≥ 3 on VSS Scale and a culture positive for *Candida* spp. that required antifungal treatment) at TOC (Week 24). Efficacy will also be assessed by other secondary efficacy and patient-reported outcomes (see [Section 9.3](#)).

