10.1.1 Study Visits

Study visits will consist of scheduled on-site visits, phone contacts, and lab visits (Acute Phase only), as well as unscheduled visits. Whenever possible, on-site visits and phone contacts will be scheduled to occur on the date of dosing (or as close to the date of dosing as possible) to facilitate reminding subjects to take their study doses. This is applicable for the Baseline (Day 1), Week 4, Week 8, Week 12, Week 16 (phone contact), and Week 20 (phone contact) visits.

If a subject is actively menstruating at an on-site study visit that requires a vaginal exam, the visit should be rescheduled as soon as the subject's period ends but in no case more than 7 days after the initially scheduled visit.

Phone contacts will be conducted to check for AEs, treatment compliance, potential recurrence, and concomitant medication use, including other antifungal agents. Unscheduled visits will be conducted anytime that there are symptoms indicating a potential recurrence or an AE.

Subjects will be instructed to visit the study center for a proper evaluation of any potential recurrence before initiating any VVC treatment. Subjects participating in the study will be strongly discouraged from self-administering any treatment for a potential recurrence.

An electronic dosing reminder system (e.g. text message) may be implemented for consenting subjects to facilitate study drug dosing compliance.

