11.2 Exclusion Criteria

A subject will be excluded from participation in the study if she meets any of the following exclusion criteria:

1. Subject has any vaginal condition other than RVVC that may interfere with the diagnosis or evaluation of response to therapy, such as suspected or confirmed concurrent causes of vulvovaginitis and/or cervicitis including bacterial vaginosis, *Trichomonas*, *Herpes* virus, *Neisseria gonorrhoeae*, *Chlamydia*, symptomatic human papillomavirus infection or other mixed infections.
2. Subject received systemic and/or topical vaginal antifungal treatment, including prescription or over-the-counter products, within 28 days prior to the Day -14 visit.
3. Subject is receiving or anticipates to require treatment with the prohibited medications (including prescription and over-the-counter medications, supplements, and herbal products) listed in [Section 21.0 \(Appendix A\)](#), during the following timeframes:
 - a. Systemic and topical vaginal antifungal treatment other than study drug and rescue medication (if needed), as specified in the protocol, anytime during the study.
 - b. Select CYP3A4/5 inducers during the 14 days prior to enrollment and during study treatment.
 - c. Select strong CYP3A4/5 inhibitors during 48 hours prior to enrollment and during study treatment.
 - d. Select P-gp substrates during the 48 hours prior to enrollment or during study treatment with ibrexafungerp.
 - e. Topical vaginal corticosteroids from 7 days prior to the Screening visit to the Week 24 (TOC) visit.
4. Subject has active menstruation at the Screening visit. **Note:** The Screening visit may be rescheduled if required.
5. Subject has a history of or an active cervical/vaginal cancer.
6. Subject has a known hypersensitivity to fluconazole or any of the components of the fluconazole or ibrexafungerp formulations.
7. Subject has a known human immunodeficiency virus infection and/or is receiving chemotherapy, has recently received immunosuppressive or systemic corticosteroid therapies, or has an illness that, in the judgment of the investigator, is serious enough to induce an immune deficiency.
8. Subject has had any major illness within 30 days before Screening.
9. Subject has participated in any other investigational study within at least 30 days (or 5.5 half-lives of the investigational product, whichever is longer) before signing the ICF.
10. Subject has received prior treatment with the study drug in a previous trial.

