13.4 Study Restrictions

There are no study restrictions other than those described in [Sections 11.2 \(Exclusion Criteria\)](#), [Section 12.2 \(Dietary Requirements\)](#) and [Section 13.2 \(Prohibited Medications\)](#).

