14.18.3 Rescue Antifungal Therapy

Subjects will be offered one dose of fluconazole 150 mg as rescue therapy. Other antifungal rescue therapy may be administered, per investigator's discretion, based on the *Candida* species reported from the culture results. All antifungal therapy administered during the study should be documented in the EDC, with the reason for use clearly indicated (i.e., Mycologically Proven Recurrence, Presumed Recurrence or Suspected Recurrence).

If a subject experiences one or more recurrences during the Study Treatment Period (i.e., a Mycologically Proven Recurrence, a Presumed Recurrence or a Suspected Recurrence), she will continue her scheduled study drug administration and will complete all scheduled visits until reaching EOFU.

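### Rescue therapy and the continue-dosing rule are not tied to the Section 7.1 ban on strong CYP3A inhibitors, so a study dose could fall within a strong-inhibitor antifungal course

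*Protocol*

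**What the plan says.** **The ban.** Protocol Section 7.1 (nonclinical experience) expects strong CYP3A inhibitors to raise ibrexafungerp levels; "therefore, the concurrent administration of ibrexafungerp with such inhibitors is prohibited". Its clinical part adds: "Ketoconazole (a strong inhibitor of CYP3A) induces a significant (5-fold) increase in ibrexafungerp exposure".

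**Rescue.** Section 14.18.3 offers a single 150 mg dose of fluconazole. It continues: "Other antifungal rescue therapy may be administered, per investigator's discretion, based on the *Candida* species reported from the culture results". It sets no CYP3A limit and does not point to Section 13.2 or Appendix A.

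**Dosing after rescue.** Section 10.1 keeps all six dosing days "regardless of recurrence or administration of antifungal medication". The synopsis, Sections 10.1.1.3.1, 10.1.1.3.3, 11.3 and 14.18.3, Table 2 footnote l and SAP Appendix 1 footnote l give the same instruction in similar terms.

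**Restrictions that sites apply.** Exclusion criterion 3a bars "antifungal treatment other than study drug and rescue medication (if needed), as specified in the protocol", so rescue is exempt from the antifungal ban, and Appendix A repeats that exemption. Criterion 3c and Section 13.2 separately bar selected strong CYP3A4/5 inhibitors. Criterion 3c runs through study treatment, and neither text exempts rescue. The Appendix A footnote limits this ban to the drugs in its table. Section 13.4 says "There are no study restrictions other than those described in" Sections 11.2, 12.2 and 13.2.

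**The concern.** Section 7.1 states a rule for the whole class, but the text that governs rescue and dosing does not carry it through. An investigator choosing a non-fluconazole agent by species is not reminded of the interaction. No text says what to do with a study dose that falls due while a subject is taking a strong inhibitor. Outside prescribing is foreseen in Section 14.18.2, which asks only for a prompt site visit with a culture.

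What is at stake is patient safety in a few subjects. The site is blinded and cannot tell whose ibrexafungerp exposure would be raised. Section 14.12 schedules no routine safety laboratory tests after Week 12, so a raised exposure at the Week 16 or Week 20 dose would have no planned laboratory check.

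**Working it through.** **1. Reading the rules together.** Suppose a subject takes a strong-inhibitor antifungal for a recurrence, and a dosing day falls within the course.

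- If the agent is listed in Appendix A, criterion 3c and Section 13.2 prohibit it, rescue or not. If it has been taken anyway, the dosing rule still says to take the study dose. The two instructions conflict and nothing says which prevails.
- If the agent is not listed, only Section 7.1 prohibits it, and Section 13.4 does not count 7.1 among the restrictions.

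Either way, following the dosing rule produces the combination that 7.1 prohibits. This does not depend on what Appendix A lists.

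**2. The Appendix A table.** As extracted, the inhibitor column names no azole; alphabetically, ketoconazole would stand between indinavir and lopinavir/ritonavir. But the names under the inducer heading continue the inhibitor column's alphabetical order, so cells have been misplaced or lost. Whether an azole is listed has to be checked in the PDF.

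**3. How often a course would cover a dosing day.** Table 1 puts the dosing days after Baseline at Days 28, 56, 84, 112 and 140. The Baseline dose cannot follow a recurrence. Assume one course per rescued subject, starting on a random day from Day 2 to Day 168: 168 − 2 + 1 = 167 possible days. A course of L days (L up to 14) covers a dosing day for 5L of these.

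- L = 1: 5/167 = 3.0%
- L = 7: 35/167 = 21.0%
- L = 14: 70/167 = 41.9%

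**4. How many subjects.** Section 18.1 plans 240 subjects at 1:1, so 120 per arm, with success rates of 65% and 43%.

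- Planned failures on ibrexafungerp: 0.35 × 120 = 42
- Planned failures on placebo: 0.57 × 120 = 68.4
- Both arms: 110.4

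Use these as stand-ins for subjects rescued by Week 24. The share given a strong inhibitor and the course length are not in the documents; assume 1% to 10% and 1 to 14 days. Ibrexafungerp subjects dosed during such a course:

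- Low: 42 × 0.01 × 5/167 = 0.013
- Middle (5%, 7 days): 42 × 0.05 × 35/167 = 0.44
- High: 42 × 0.10 × 70/167 = 1.76

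**5. Doses lost to a skip rule.** At the high setting, over both arms: 110.4 × 0.10 × 70/167 = 4.6 dosing days. Planned dosing days: 240 × 6 = 1,440. The share is 4.6/1,440 = 0.3%, before any washout.

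**The case against.** The strongest reply is that the protocol already covers this. Section 13.4 counts Sections 11.2 and 13.2, which bar listed strong inhibitors with no exemption for rescue. Section 14.18.2 sends the recording of antifungal treatment to Section 14.21, which refers to Section 13.0 for prohibited medications. Site visits and phone contacts are placed on or near dosing days where possible, and phone contacts check "potential recurrence, and concomitant medication use, including other antifungal agents". Section 11.3 lets the investigator or sponsor withdraw a subject, or stop study drug, in her interest. All of this stands, and a reader who infers that the operative rules leave rescue free of any CYP3A restriction would be wrong. It does not remove the instruction to keep dosing, nor say what happens to the dose.

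Four other inferences go too far:

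- *Appendix A omits azoles.* The alphabetical gap is suggestive, but a damaged table cannot show an omission.
- *Itraconazole is a missing strong inhibitor.* The documents describe only ketoconazole as strong. Section 7.1 mentions itraconazole only in saying that "oral azoles (e.g., ketoconazole, itraconazole, and fluconazole) have been studied showing benefit in preventing recurrences of VVC".
- *Ketoconazole is a usual rescue choice here.* That sentence concerns maintenance regimens; the named rescue is fluconazole.
- *A 5-fold exposure equals five times the dose.* Section 7.1 gives neither the exposure measure nor the ketoconazole regimen. It also reports that single oral doses up to 1600 mg were generally well tolerated.

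**Conclusion.** The inconsistency is real and minor. One part of the protocol prohibits a combination that another part, followed literally, would produce. Correcting it is a cheap improvement for patient safety.

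The illustrative size is from well under one to about two ibrexafungerp subjects (0.013 to 1.76). A reader might take 42 rescued subjects, or 1.8 affected, as ceilings. They are not. They rest on planning success rates, one course per subject, uniform start days, and assumed shares and course lengths. The planned failures include subjects who fail through missing data and are never rescued, which pushes the figure down. Against that, the endpoints allow for four or more episodes, which pushes it up.

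A reader might also fear for the primary result. Under SAP Section 8.1, a subject treated with an antifungal for a VVC episode before the Week 24 visit is already a clinical failure, so neither a later study dose nor a skipped one changes her primary outcome. With so few subjects, no effect is expected on the other efficacy comparisons or on the adverse-event comparison.

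**What to change.** 1. Add one sentence to Section 14.18.3: *Rescue therapy during the Study Treatment Period must not include strong CYP3A4/5 inhibitors (e.g., ketoconazole); Section 13.2 and Appendix A apply to rescue agents.*
2. Check the Appendix A table in the PDF and add ketoconazole to the inhibitors if it is absent.
3. Qualify the continue-dosing rule wherever it appears: the synopsis, Sections 10.1, 10.1.1.3.1, 10.1.1.3.3, 11.3 and 14.18.3, Table 2 footnote l, and SAP Appendix 1 footnote l. In both arms, a study dose that falls within a strong CYP3A inhibitor course is skipped and recorded as missed, and the medical monitor is contacted. The sponsor sets any washout, because the documents give none for rescue. Changing only some of these places would create a new inconsistency.

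The cost is a text edit, slightly fewer rescue options and, rarely, a missed dose (about 4.6 of 1,440 dosing days at the high setting, before any washout). No visits, samples or analyses are added. A dosing day is 4 tablets, so one skipped day leaves 20 of 24 (83.3%), still in the upper compliance class of SAP Section 7.2.2.2; two leave 16 of 24 (66.7%), in the lower class. Applying the rule in both arms protects the blind.

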14.19 Collection of Blinded Study Drug Supplies and Evaluation of Treatment Compliance

Treatment compliance with double-blind study drug will be reviewed by the investigator or designee at all study visits during the Study Treatment Period, including both on-site visits and phone contacts. Subjects (or subjects' legal representatives, if applicable) will be instructed to bring all bottles (including empty bottles) of study medication with them at all visits to assess medication compliance. Empty bottles will be collected at Week 12 and Week 24 (TOC). Further details are available in [Section 12.5](#).

14.20 Vital Signs

Vital signs, including blood pressure (systolic and diastolic), heart rate, respiratory rate and body temperature will be measured at all on-site scheduled and unscheduled visits.

14.21 Prior and Concomitant Medication Review

All medications (including prescription and over-the-counter medications, supplements, and herbal products) taken from 28 days before Screening through the Week 24 (TOC) visit will be recorded on the eCRF. Only the use of other antifungal medications, medications used to treat vaginal bacterial or parasitic infections, topical vaginal medications or medications to treat a study-drug related AE will be recorded after the TOC visit through the last study visit (Week 36 [EOFU]). Start and stop dates of concomitant medications will be recorded on the eCRF. Prior and concomitant medications will be reviewed and recorded at all scheduled and unscheduled study visits.

See [Section 13.0](#) for prohibited medications, medications to be administered with caution and further details for non-study treatments.

14.22 Adverse Event Monitoring

AEs will be recorded and reviewed at all scheduled and unscheduled study visits from the time the ICF is signed (Screening) through Week 24 (TOC). New AEs starting after Week 24 and until Week 36 will be recorded only if they led to the use of other antifungal medications or topical vaginal treatment, if they are a vaginal bacterial or parasitic infection, or if they are deemed related to the previously administered study drug. See [Section 16.0](#) for further reference.

